While we have presented ranges of detectable effect sizes for our models even accounting for 20% missing data, we will investigate all missing data. Initially, the likelihood of missingness will be checked to see whether it is associated with any of the covariates or outcomes. Missing data are usually categorized as missing completely at random (MCAR), missing at random (MAR), or missing not at random (MNAR). Complete case analysis assumes that data are MCAR, though it is rare that data really are MCAR. Missing data can potentially weaken the validity of results and conclusions. A number of methods have been developed for dealing with missing data. Multiple imputation is a method to deal with missing data, which accounts for the uncertainty associated with missing data. Multiple imputation is implemented in our statistical software (SAS and Stata) under the MAR assumption and provides unbiased and valid estimates of associations based on information from the available data. The method affects the coefficient estimates for variables with missing data and also the estimates for other variables with no missing data. We will investigate the nature of our missing data, and if an assumption of MCAR is invalid, we will utilize multiple imputation methods.

Complete datasets will be created using the multiple imputation by chained equations method, and results across imputed datasets will be combined using Rubin's method.² Results from this approach will be compared with those that obtain when we use only observations with complete data. This was done only for outcomes assessed in evening report surveys because those provided known missing data (i.e., people did not file a report). We were unable to do this for cigarette survey data that required participants to indicate when they were smoking; hence, the missingness of these observations was not known (i.e., we could not determine whether data were "missing" because people did not smoke vs. because they did not report a smoking session). Consistency of results across these approaches will be interpreted as providing stronger evidence of the model results found than in the case of the results depending on the approach used. We will report results of these additional analyses (see following tables, below) and our interpretation of them in our papers.

Sensitivity Analysis

In addition to imputing missing data, we will also investigate the sensitivity of models to weighted analyses. Probability weights will be generated to allow inference from our samples that will be valid for the general population of smokers across the United States. Comparisons of results and inference for weighted and unweighted analyses will allow us to discuss any limitations of our sample, and what differences might exist between our sample and the general population of interest.

REFERENCES

- 1. Cohen J. A power primer. Psychological Bulletin 1992;112(1):155-59.
- 2. Rubin D. Multiple imputation after 18+ years. Journal of the American Statistical Association 1996;**91**:473-89.

Appendix 1. Results for primary and secondary outcomes that are not specific to hypothesized effects and, therefore, not in the data tables

Table 1. Hypothesis 1: Results for outcomes not specific to hypothesized effects

Outcome Variable name	Coef*	SE	95% CI LB	95% CI UB	p-value
Worry About Harms from Smoking ¹	0.77	0.59	-0.38	1.92	0.19
Strength of Feeling About Smoking ²	-0.70	0.48	-1.64	0.23	0.14
Satisfaction From Smoking ¹	-0.38	0.39	-1.15	0.39	0.33
Cognitive Elaboration of Smoking Benefits ³	-0.09	0.30	-0.68	0.49	0.76
Cognitive Elaboration of Smoking Harms ³	0.59	0.34	-0.08	1.26	0.08
Perceived Susceptibility to Smoking Harms ⁴	0.71	0.46	-0.19	1.61	0.12

^{*}All results from ordered logistic regression mixed effects models

Table 2. Hypothesis 2: Results for outcomes not specific to hypothesized effects

Outcome Variable name	Coef*	SE	95% CI LB	95% CI UB	p-value
Self-efficacy to Quit Smoking ¹	-0.26	0.51	-1.25	0.73	0.60
Self-efficacy to Cut Down on Smoking ¹	-0.37	0.49	-1.33	0.59	0.45
Strength of Hopefulness About Quitting ¹	-0.55	0.66	-1.85	0.75	0.41
Cognitive Elaboration of Cessation Benefits ²	-0.40	0.34	-1.08	0.27	0.24
Response Efficacy ³	0.09	0.39	-0.67	0.85	0.82

^{*}All results from ordered logistic regression mixed effects models

Table 3. Hypothesis 3. Results for outcomes not specific to hypothesized effects

Outcome Variable name	Coef*	SE	95% CI LB	95% CI UB	p-value
Worry About Harms from Smoking ¹	-1.22	0.85	-2.89	0.44	0.15
Strength of Feeling About Smoking ²	0.23	0.69	-1.12	1.57	0.74
Satisfaction From Smoking ¹	-0.04	0.57	-1.16	1.07	0.94
Cognitive Elaboration of Smoking Benefits ³	-0.20	0.43	-1.04	0.65	0.65
Cognitive Elaboration of Smoking Harms ³	-0.72	0.49	-1.69	0.25	0.15
Perceived Susceptibility to Smoking Harms ⁴	-1.12	0.66	-2.40	0.17	0.09
Expressed Reactance Against Messages ⁵	1.21	0.78	0.35	4.25	0.76

^{*}All results from ordered logistic regression mixed effects models except for "Expressed reactance" which shows Odds Ratio for logistic regression mixed effects model.

^{1.} response options=1 Not at all – 7 Extremely; 2. response options=1 very BAD – 7 Very GOOD; 3. response options=1 Not at all – 7 All the time; 4. 1 No chance – 7 Certain to happen.

^{1.} response options=1 Not at all -7 Extremely; 2. response options= 1 Not at all -7 All the time; 3. 1 No chance -7 Certain to happen.

^{1.} response options=1 Not at all - 7 Extremely; 2. response options=1 very BAD - 7 Very GOOD; 3. response options=1 Not at all - 7 All the time; 4. 1 No chance - 7 Certain to happen. 5. Response options=yes, no

Table 4. Hypothesis 4. Results for outcomes not specific to hypothesized effects

Outcome Variable name	Coef*	SE	95% CI LB	95% CI UB	p-value
Worry About Harms from Smoking ¹	-0.12	0.84	-1.77	1.53	0.88
Strength of Feeling About Smoking ²	-0.08	0.68	-1.41	1.26	0.91
Satisfaction From Smoking ¹	-0.07	0.56	-1.17	1.03	0.90
Cognitive Elaboration of Smoking Benefits ³	0.23	0.49	-0.74	1.19	0.65
Cognitive Elaboration of Smoking Harms ³	0.18	0.49	-0.78	1.14	0.71
Perceived Susceptibility to Smoking Harms ⁴	-0.15	0.66	-1.45	1.15	0.82

^{*}All results from ordered logistic regression mixed effects models

Table 5a. Hypothesis 5a. Results for outcomes not specific to hypothesized effects

Outcome Variable name	Coef*	SE	95% CI LB	95% CI UB	p-value
Self-efficacy to Quit Smoking ¹	0.50	0.97	-1.41	2.41	0.61
Self-efficacy to Cut Down on Smoking ¹	0.35	0.95	-1.50	2.21	0.71
Strength of Hopefulness About Quitting ¹	1.18	1.25	-1.27	3.62	0.35
Satisfaction From Smoking ¹	-0.31	0.79	-1.85	1.24	0.70
Cognitive Elaboration of Smoking Benefits ²	0.54	0.60	-0.64	1.72	0.37
Cognitive Elaboration of Cessation Benefits ²	0.37	0.67	-0.94	1.69	0.58
Response Efficacy ³	-0.42	0.77	-1.92	1.09	0.59

^{*}All results from ordered logistic regression mixed effects models

Table 5b. Hypothesis 5b. Results for outcomes not specific to hypothesized effects

Outcome Variable name	Coef*	SE	95% CI LB	95% CI UB	p-value
Self-efficacy to Quit Smoking ¹	0.57	1.38	-2.15	3.28	0.68
Self-efficacy to Cut Down on Smoking ¹	0.08	1.35	-2.56	2.73	0.95
Strength of Hopefulness About Quitting ¹	-1.38	1.77	-4.84	2.09	0.44
Satisfaction From Smoking ¹	-0.05	1.12	-2.25	2.15	0.97
Cognitive Elaboration of Smoking Benefits ²	1.67	0.86	-0.01	3.35	0.05
Cognitive Elaboration of Cessation Benefits ²	0.88	0.96	-1.00	2.75	0.36
Response Efficacy ³	1.45	1.10	-0.70	3.60	0.19

^{*}All results from ordered logistic regression mixed effects models

^{1.} response options=1 Not at all -7 Extremely; 2. response options=1 very BAD -7 Very GOOD; 3. response options= 1 Not at all -7 All the time; 4. 1 No chance -7 Certain to happen.

^{1.} response options=1 Not at all -7 Extremely; 2. response options= 1 Not at all -7 All the time; 3. 1 No chance -7 Certain to happen.

^{1.} response options=1 Not at all $-\overline{7}$ Extremely; 2. response options=1 Not at all $-\overline{7}$ All the time; 3. 1 No chance $-\overline{7}$ Certain to happen.

Table 6a-Edu. Hypothesis 6a (moderation by education): Results for outcomes not specific to hypothesized effects

Outcome Variable name	В	SE	95% CI LB	95% CI UB	p-value
Worry About Harms from Smoking ¹	1.30	1.19	-1.04	3.65	0.27
Strength of Feeling About Smoking ²	-0.89	0.96	-2.78	1.00	0.35
Satisfaction From Smoking ¹	-0.61	0.81	-2.19	0.97	0.45
Cognitive Elaboration of Smoking Benefits ³	0.16	0.61	-1.02	1.35	0.79
Cognitive Elaboration of Smoking Harms ³	1.01	0.70	-0.36	2.38	0.15
Perceived Susceptibility to Smoking Harms ⁴	0.75	0.93	-1.07	2.56	0.42
Expressed Reactance Against Messages ⁵	3.52	3.44	0.52	23.95	0.20

^{*}All results from ordered logistic regression mixed effects models except for "Expressed reactance" which shows Odds Ratio for logistic regression mixed effects model.

Table 6a-Lit. Hypothesis 6a (moderation by health literacy): Results for outcomes not specific to hypothesized effects

Outcome Variable name	В	SE	95% CI LB	95% CI UB	p-value
Worry About Harms from Smoking ¹	0.25	1.27	-2.25	2.75	0.84
Strength of Feeling About Smoking ²	0.63	1.03	-1.39	2.64	0.54
Satisfaction From Smoking ¹	0.91	0.85	-0.75	2.58	0.28
Cognitive Elaboration of Smoking Benefits ³	-0.03	0.66	-1.32	1.26	0.97
Cognitive Elaboration of Smoking Harms ³	0.35	0.75	-1.12	1.82	0.64
Perceived Susceptibility to Smoking Harms ⁴	0.16	1.00	-1.80	2.12	0.87
Expressed Reactance Against Messages ⁵	6.78	7.25	0.83	55.10	0.07

^{*}All results from ordered logistic regression mixed effects models except for "Expressed reactance" which shows Odds Ratio for logistic regression mixed effects model.

Table 6a-DD. Hypothesis 6a (moderation by delayed discounting): Results for outcomes not specific to hypothesized effects

Outcome Variable name	В	SE	95% CI LB	95% CI UB	p-value
Worry About Harms from Smoking ¹	2.71	1.19	0.39	5.04	0.02
Strength of Feeling About Smoking ²	-1.11	0.95	-2.96	0.74	0.24
Satisfaction From Smoking ¹	-2.03	0.78	-3.57	-0.49	0.01
Cognitive Elaboration of Smoking Benefits ³	0.06	0.60	-1.12	1.23	0.92
Cognitive Elaboration of Smoking Harms ³	1.61	0.69	0.26	2.95	0.69
Perceived Susceptibility to Smoking Harms ⁴	2.38	0.92	0.58	4.18	0.01
Expressed Reactance Against Messages ⁵	2.10	2.13	0.29	15.26	0.46

^{*}All results from ordered logistic regression mixed effects models except for "Expressed reactance" which shows Odds Ratio for logistic regression mixed effects model.

^{1.} response options=1 Not at all - 7 Extremely; 2. response options=1 very BAD - 7 Very GOOD; 3. response options=1 Not at all - 7 All the time; 4. 1 No chance - 7 Certain to happen. 5. Response options=yes, no

^{1.} response options=1 Not at all – 7 Extremely; 2. response options=1 very BAD – 7 Very GOOD; 3. response options= 1 Not at all – 7 All the time; 4. 1 No chance – 7 Certain to happen. 5. Response options=yes, no

^{1.} response options=1 Not at all - 7 Extremely; 2. response options=1 very BAD - 7 Very GOOD; 3. response options= 1 Not at all - 7 All the time; 4. 1 No chance - 7 Certain to happen. 5. Response options=yes, no

Table 6b-Edu. Hypothesis 6b (moderation by education): Results for outcomes not specific to hypothesized effects

Outcome Variable name	В	SE	95% CI LB	95% CI UB	p-value
Worry About Harms from Smoking ¹	1.22	1.71	-2.14	4.58	0.48
Strength of Feeling About Smoking ²	-0.79	1.38	-3.51	1.92	0.57
Satisfaction From Smoking ¹	-0.51	1.16	-2.78	1.76	0.66
Cognitive Elaboration of Smoking Benefits ³	-1.30	0.86	-2.99	0.39	0.13
Cognitive Elaboration of Smoking Harms ³	-0.15	0.99	-2.10	1.79	0.88
Perceived Susceptibility to Smoking Harms ⁴	0.95	1.32	-1.64	3.54	0.47
Expressed Reactance Against Messages ⁵	0.81	1.15	0.05	12.96	0.88

^{*}All results from ordered logistic regression mixed effects models except for "Expressed reactance" which shows Odds Ratio for logistic regression mixed effects model.

Table 6b-Lit. Hypothesis 6b (moderation by health literacy): Results for outcomes not specific to hypothesized effects

Outcome Variable name	В	SE	95% CI LB	95% CI UB	p-value
Worry About Harms from Smoking ¹	-0.48	1.86	-4.12	3.15	0.79
Strength of Feeling About Smoking ²	-0.39	1.50	-3.32	2.55	0.80
Satisfaction From Smoking ¹	-1.27	1.24	-3.70	1.15	0.30
Cognitive Elaboration of Smoking Benefits ³	-0.33	0.95	-2.18	1.53	0.73
Cognitive Elaboration of Smoking Harms ³	-0.73	1.08	-2.85	1.39	0.50
Perceived Susceptibility to Smoking Harms ⁴	-0.38	1.44	-3.20	2.45	0.79
Expressed Reactance Against Messages ⁵	2.05	3.40	0.08	52.63	0.66

^{*}All results from ordered logistic regression mixed effects models except for "Expressed reactance" which shows Odds Ratio for logistic regression mixed effects model.

Table 6b-DD. Hypothesis 6b (moderation by delayed discounting): Results for outcomes not specific to hypothesized effects

Outcome Variable name	В	SE	95% CI LB	95% CI UB	p-value	1
Worry About Harms from Smoking ¹	-0.05	1.71	-3.41	3.31	0.98	
Strength of Feeling About Smoking ²	3.76	1.37	1.08	6.45	0.01	
Satisfaction From Smoking ¹	2.52	1.13	0.30	4.75	0.03	
Cognitive Elaboration of Smoking Benefits ³	1.03	0.86	-0.67	2.72	0.23	
Cognitive Elaboration of Smoking Harms ³	-0.60	0.99	-2.54	1.34	0.54	
Perceived Susceptibility to Smoking Harms ⁴	-0.17	1.32	-2.76	2.41	0.89	
Expressed Reactance Against Messages ⁵	0.12	0.19	0.01	2.54	0.17	

^{*}All results from ordered logistic regression mixed effects models except for "Expressed reactance" which shows Odds Ratio for logistic regression mixed effects model.

^{1.} response options=1 Not at all - 7 Extremely; 2. response options=1 very BAD - 7 Very GOOD; 3. response options=1 Not at all - 7 All the time; 4. 1 No chance - 7 Certain to happen. 5. Response options=yes, no

^{1.} response options=1 Not at all – 7 Extremely; 2. response options=1 very BAD – 7 Very GOOD; 3. response options= 1 Not at all – 7 All the time; 4. 1 No chance – 7 Certain to happen. 5. Response options=yes, no

^{1.} response options=1 Not at all - 7 Extremely; 2. response options=1 very BAD - 7 Very GOOD; 3. response options=1 Not at all - 7 All the time; 4. 1 No chance - 7 Certain to happen. 5. Response options=yes, no

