We use the numbers in Table 4 as inputs for independent observations in deriving the detectable effect. In what follows, we report ranges of detectable effect sizes from 0% to 20% missing data in complete-case analyses. This presentation notwithstanding, our data analysis will employ multiple imputation methods to replace missing data, and we will investigate sensitivity models to determine whether missingness is related to any of the outcomes or covariates (See **Missing Data**, below).

Alpha: Modifications of the level of significance are considered using Bonferroni adjustment to maintain an overall 0.05 level of significance. As most of our hypotheses involve assessing 6 primary outcomes for each of the two data types, we use a Bonferroni-corrected $\alpha = 0.05/6 = 0.0083$.

Effects size referents: We follow Cohen's standardized effect sizes of small=0.20, medium=0.50, and large=0.80.¹ Standardized effect sizes are absolute differences divided by the standard deviation.

Power: Power was fixed to 80% in all analyses.

Analyses: Most detectable effect sizes were calculated using PASS 2012 software from NCSS (Kayesville, Utah). The only exception is for a hypothesis of mediation. In that case, we used the *powerMediation* package for *R* software. Specifically, we utilized the *minEffect.SLR* method to determine the minimum detectable slope (effect).

All detectable effect sizes were calculated for power=80% and stated level of significance. Furthermore, we assessed detectable effect sizes for the planned data collection design, up to 10% missing data, and up to 20% missing data (see Table 4).

Statistical design:

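### For evening outcomes, agreement between multiple imputation and the filed-data mixed model shows robustness within missing-at-random only; the plan should say so and add an analysis that probes informative non-response

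*SAP*

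**What the plan says.** The SAP's Statistical design section analyses repeated outcomes with mixed effects generalised linear models. Model 1 indexes the outcome by person and repeated measure and carries a person effect, so each filed evening is one row, up to 14 per person. Table 3 lists talk and forgo/stub as primary and marks them for every hypothesis. The Protocol's evening survey collects both, once a day, about the previous 24 hours.

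The Missing Data section says of the unimputed analysis: "Complete case analysis assumes that data are MCAR, though it is rare that data really are MCAR". Of imputation it says: "Multiple imputation is implemented in our statistical software (SAS and Stata) under the MAR assumption". It sets a condition, "if an assumption of MCAR is invalid, we will utilize multiple imputation methods", then describes the method: "Complete datasets will be created using the multiple imputation by chained equations method". The comparison is: "Results from this approach will be compared with those that obtain when we use only observations with complete data". It is confined to evening-report outcomes, because an unlogged cigarette cannot be told apart from one not smoked. The interpretation rule follows: "Consistency of results across these approaches will be interpreted as providing stronger evidence of the model results found"; the sentence goes on to rank this above results that change with the method.

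Missing not at random (MNAR) is named as a category, but no analysis allows for it. The Sensitivity Analysis section adds only weighting to US smokers. In the section on power assumptions, below Table 4, the SAP says without condition that "our data analysis will employ multiple imputation methods to replace missing data".

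**The concern.** The rule gains its force from the idea that two analyses resting on different assumptions (MCAR and MAR) reach the same answer. If both rest on MAR and draw on the same data, agreement is what one expects in any case. It then carries no information about the main hazard for a diary outcome, which is that an evening goes unreported because of what happened that day.

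Two primary outcomes are affected, and the SAP commits to reporting and interpreting the comparison in its papers. A reader could take the agreement as reassurance that it cannot give. The unconditional sentence on imputation in the power section also sits badly with the conditional, comparative use in Missing Data.

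**Working it through.** The plan states no figure for this point, so there is none to reproduce. The check has three parts.

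**1. What each analysis assumes.** With filed values y_obs, unfiled values y_mis, arm and covariates Z:
- The mixed model maximises f(y_obs | arm, Z) over all filed rows. This is valid under MAR given arm, Z and the observed outcomes; MCAR is not needed.
- Imputation draws y_mis from f(y_mis | y_obs, arm, Z) and refits the same model. If the predictors are the same, this extends the same likelihood, and the pooled estimate should reproduce the mixed-model estimate up to simulation noise.
- If unfiled evenings differ from filed ones given y_obs, arm and Z, neither analysis sees it. The SAP's check of missingness against outcomes and covariates cannot use unreported values, so it can reject MCAR but cannot separate MAR from MNAR.

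**2. Simulation, continuous outcome (SD 1, true effect 0).** Inputs from the SAP: 160 persons per side and 14 evenings (Table 4); 20% missing, the largest fraction in Table 4; within-person correlation 0.40 (planned) and 0.73 (mean observed). Assumed: in one arm the logit of missingness falls by 1 or 2 per SD of the unreported value (MNAR), or depends on the last observed value (MAR). There were 60 replicates per scenario, with chained equations, 10 imputations and Rubin's rules. Pairs are mixed model / imputation.

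| Correlation | Mechanism | Bias (SD) | Mean absolute gap | Mean SE | Rejected at 0.05 |
|---|---|---|---|---|---|
| 0.40 | MCAR | +0.002 / +0.002 | 0.0036 | 0.075 | 2% / 2% |
| 0.40 | MAR | -0.000 / +0.001 | 0.0054 | 0.076 | 3% / 3% |
| 0.40 | MNAR, slope 1 | +0.122 / +0.123 | 0.0047 | 0.072 | 28% / 27% |
| 0.40 | MNAR, slope 2 | +0.191 / +0.190 | 0.0044 | 0.069 | 78% / 78% |
| 0.73 | MCAR | +0.000 / +0.001 | 0.0024 | 0.097 | 3% / 3% |
| 0.73 | MAR | +0.000 / +0.000 | 0.0028 | 0.097 | 8% / 7% |
| 0.73 | MNAR, slope 1 | +0.056 / +0.056 | 0.0022 | 0.097 | 5% / 5% |
| 0.73 | MNAR, slope 2 | +0.108 / +0.107 | 0.0035 | 0.092 | 23% / 22% |

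(Mean SE is for the mixed model; imputation was within 0.001.) The MAR rows confirm that the filed-data mixed model does not need MCAR. The gap is as small when both estimates are wrong as when both are right. The two analyses reached the same decision in 95 to 100% of replicates.

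**3. Simulation, binary outcome, as for talk and forgo/stub.** Logistic random-intercept model, 184 v 184 persons, 14 evenings, 20% unfiled, no true effect, 100 replicates per scenario, one arm skipping evenings whose answer would be no (slopes 1 and 2, assumed).
- Correlation 0.40: log-odds bias 0.20 / 0.20 and 0.35 / 0.35; mean gap 0.01; rejections 21% / 21% and 50% / 48%, against 3% / 3% without informative skipping.
- Correlation 0.73: bias 0.16 / 0.17 and 0.29 / 0.28; mean gap 0.04 to 0.05 against an SE of about 0.33; rejections 13% / 11% and 18% / 17%, against 7% / 7%.

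On the probability scale the size is set by the assumption. If 20% of one arm's evenings are unfiled and the true rate on them is 10 points below that on filed evenings, both analyses overstate that arm by about 0.20 × 10 = 2 points.

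**The case against.** - **The sentence is comparative.** It ranks agreement above disagreement and claims neither freedom from bias nor robustness to MNAR. This stands. The criticism is of what a reader will take from it.
- **Agreement is not guaranteed.** The SAP does not list the imputation predictors. Same-day cigarette surveys (motivation, worry, efficacy) may exist on an evening without a report, and they are not among the example covariates. In a simulation with 184 v 184 persons, correlation 0.73 and MNAR slope 1, a same-day auxiliary correlated 0.5 to 0.7 with the day's deviation widened the mean gap from 0.002 to 0.014-0.028 SD. It cut imputation bias to 0.046-0.038, against 0.061-0.066 for the mixed model. The gap was still below the SE, so the comparison can be informative but is weak. Rows lost to missing covariates could also separate the two methods.
- **It is not the only check.** Missingness is first examined against covariates and outcomes. True, but that cannot exclude MNAR.
- **A reader might infer that the MCAR condition makes the headline result data-dependent.** The documents do not support that. The SAP's version note discusses this work as sensitivity analysis, Missing Data calls it additional, and the Sensitivity Analysis section groups it with the weighted analyses. What remains is one loose sentence in the power section and a condition that the mixed model does not need.
- **A reader might set a bias of about 0.07 SD against the 0.07-0.08 that Table 6 calls detectable for Type 2 outcomes.** That is the wrong row. Evening outcomes are Type 1, for which Table 6 gives 0.15-0.17 for H1 and H2.

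**Conclusion.** The point holds in a limited form. For evening-report outcomes, the comparison sets one MAR analysis beside another, and the MCAR description does not fit the mixed model actually used. Agreement therefore supports robustness within MAR and says almost nothing about informative non-response, which no planned analysis addresses.

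This rests on reading the comparator as dropping unfiled evenings, not whole persons, and on the two analyses sharing essentially the same information. The simulated biases (0.056 to 0.108 SD at correlation 0.73, 0.122 to 0.191 at 0.40) show what could go unnoticed under assumed mechanisms. Only the most extreme exceeds the Type 1 range of 0.15-0.17. A reader might infer that the reported evening results are biased; the documents give no basis for that, nor for a direction or size. The change is worth making because it is cheap and replaces an uninformative rule with an informative one.

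**What to change.** 1. In Missing Data, reword the consistency sentence so that agreement is reported as robustness within MAR, and drop the MCAR description of the mixed-model comparator.
2. Add a delta-adjusted imputation for talk and forgo/stub. Impute in a way that keeps within-person correlation (a person effect, or the 14 evenings as joint variables) and list the predictors, including whether same-day cigarette-survey answers enter. Shift the log-odds on unfiled evenings separately by arm over a stated range, for example -1 to +1 (odds ratios of about 0.37 to 2.72). Report the shift at which the H1 or H2 conclusion changes. Label the analysis post hoc: the SAP is dated December 2022 and already contains results, and the last debrief was in June 2021.
3. Align the sentence below Table 4 with Missing Data. State that the mixed model on filed evenings is primary and imputation is a sensitivity analysis, with no MCAR condition deciding whether it is run.

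The cost is a few sentences and a modest analysis of existing data. The downside is that the delta range is a judgement: the documents offer no basis for one, so it must be stated and justified.

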4 STUDY POPULATION

Participant eligibility:

- Legal age to purchase cigarettes, which started at 18 but was changed to 21 years old (December 20, 2019) after the federal government increased the legal age of tobacco purchase;
- Smoked at least 100 cigarettes in their life;
- Smoked at least 10 cigarettes per day, to ensure exposure to four rotating labels in each treatment condition;
- Exhaled carbon monoxide of at least 8ppm to confirm smoking status, using COVITA. After the onset of COVID-19, this criterion was eliminated due to concerns about COVID transmission while using the COVITA device.

Participant ineligibility:

- Use of e-cigarettes, other forms of smoked tobacco (cigars, water pipe, hookah, cigarillos, little cigars, pipe), or smokeless tobacco products (chewing tobacco, snuff, dip) in the last month to minimize issues of cross-product substitution, as the study was not designed to address this issue;
- Living with someone else who has participated in or was currently participating in this two-week study, in order to prevent exposure to the study stimuli;
- Pregnant or considering becoming pregnant;
- After the onset of COVID-19 data collection, participants who reported having experienced symptoms or having been exposed to COVID-19 in the prior 30 days.

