- 115. IARC. IARC Handbooks of Cancer Prevention: Tobacco Control. Volume 12. Methods for Evaluating Tobacco Control Policies. Lyon, France: International Agency for Research on Cancer 2009.
- 117. RTI. PhenX Toolkit: Tobacco Regulatory Science RTP, North Carolina: Research Triangle Institue, International; 2017 [Available from: https://www.phenxtoolkit.org/index.php?pageLink=browse.conceptualgroups&id=3456&breadcrumbs=34 56.
- 118. NIDA. PATH Study Data Collection Instruments (Wave 3). Bethesda, MD: National Institute of Drug Abuse, National Institutes of Health, 2015.

EMA Insert Study – Baseline Survey: July 10, 2020

NOTE: After the onset of COVID-19, the questionnaire was modified to include additional questions related to COVID (shown below) but was otherwise the same as the survey used before COVID-19 onset.

Var ID	Eligibility
DE01	How old are you? [Enter age] [If <21, NOT ELIGIBLE]
SB01	Have you smoked at least 100 cigarettes in your life?1. Yes2. No
SB02	In the past 30 days, did you smoke every day, some days, or not at all? Every day Some days [NOT ELIGIBLE] Did not smoke [NOT ELIGIBLE]
ND04	On average, how many cigarettes do you smoke each day, including both factory-made and roll-your- own cigarettes? [Enter number of cigarettes] [If <10, NOT ELIGIBLE]
NP01	Vaping products (often called e-cigarettes) are devices that heat a liquid only, but do NOT contain any actual tobacco. The liquid often contains nicotine and may be tobacco-flavored or many other flavors. The liquid that the vaping device heats may be in a cartridge or pod, or it may come separately in a bottle. Examples include: Juul, blu and NJOY]. Image: the past 30 days, did you use a vaping product or e-cigarette? 1, Yes [NOT ELIGIBLE] 2, No
NP02	During the past 30 days, did you use any form of smoked tobacco products other than cigarettes (e.g. cigars, water pipe, hookah, cigarillos, little cigars, pipe)? 1. Yes [NOT ELIGIBLE] 2. No
NP03	During the past 30 days, did you use any form of smokeless tobacco products (e.g. chewing tobacco, snuff, dip)? 1. Yes [NOT ELIGIBLE]

Part 1: Online survey (self-administered online)

	2. No
COVID-19*	Have you or anyone in your household tested positive for COVID-19 in the last 30 days?
	1. Yes [NOT ELIGIBLE]
	2. No

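### The weighted sensitivity analysis claims validity for all US smokers, but eligibility gives several groups of smokers no chance of inclusion, so the claim should be limited to eligible smokers

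*SAP*

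**What the plan says.** **The claim.** SAP, Sensitivity Analysis: probability weights are to make inference from the sample "valid for the general population of smokers across the United States". The next sentence says that comparing weighted with unweighted results "will allow us to discuss any limitations of our sample, and what differences might exist between our sample and the general population of interest". The section does not limit the target to people who could have entered the trial. It names no reference data, weighting variables or weighting method.

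**Who could enter.** Protocol section 4 (Study Population) requires at least ten cigarettes a day: "Smoked at least 10 cigarettes per day, to ensure exposure to four rotating labels in each treatment condition". It makes ineligible anyone with past-month "Use of e-cigarettes, other forms of smoked tobacco (cigars, water pipe, hookah, cigarillos, little cigars, pipe), or smokeless tobacco products", and gives as the reason "to minimize issues of cross-product substitution, as the study was not designed to address this issue". It also excludes those who are pregnant or considering pregnancy. In the eligibility part of the baseline survey appended to the protocol, the item on past-30-day smoking frequency screens out non-daily smokers: "Some days [NOT ELIGIBLE". A note at the head of that survey says that only COVID questions were added after the onset of COVID-19, so the item is read here as applying throughout.

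**How people were found.** Protocol section 4.1 describes social-media adverts and flyers in Columbia SC, and intercepts at smoke shops in six New York locations. After the onset of COVID-19 it describes Facebook advertising only, in named cities of South Carolina and New York plus Charlotte NC. In that later period, men and people intending to quit within six months were given priority to meet quotas.

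**The concern.** A survey weight scales up a sampled person to stand for similar people who were not sampled. That requires every kind of person in the target population to have had some chance of selection. The eligibility rules set that chance to zero for lighter smokers, non-daily smokers, users of other tobacco products or e-cigarettes, and those pregnant or considering pregnancy. If the sample is weighted to totals for all US smokers, daily smokers of ten or more with no other product must stand in for all of them.

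The weighted result is also the one that a policy reader would look to. The protocol's rationale is national: it speaks of some 40 million US smokers and of the FDA's authority over inserts. If weighted and unweighted estimates agree, that agreement could be read as evidence that the findings carry over to smokers in general. The design cannot supply that evidence.

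**Working it through.** The SAP gives no figure for this analysis, so there is none to reproduce. The check is one of coverage, followed by an illustration of scale.

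**1. Coverage.** For each group in the claimed target, is the chance of inclusion above zero?

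| Group of US smokers | Source | Chance of inclusion |
|---|---|---|
| Under 10 cigarettes a day | Protocol 4; baseline survey, cigarettes-per-day item | Zero |
| Some-day smokers | Baseline survey, frequency item | Zero |
| Past-month e-cigarette, other smoked or smokeless tobacco use | Protocol 4; baseline survey | Zero |
| Pregnant or considering pregnancy | Protocol 4 | Zero |
| Eligible smokers | Protocol 4.1 | Unknown (convenience recruitment) |

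An inverse-probability weight is 1/p and is undefined at p = 0. For eligible smokers p is unknown and would have to be modelled. The age limit (raised from 18 to 21 in December 2019), the carbon monoxide threshold (dropped after the onset of COVID-19) and the COVID exclusions (added after it) each changed during the trial. They are left out of the table because they did not shut a group out for the whole period.

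**2. What the weights can recover.** Let q be the share of US smokers in the excluded groups, d_elig the effect in eligible smokers and d_excl the effect in excluded smokers. Then

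population effect = (1 − q) × d_elig + q × d_excl.

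At best the weighted estimate recovers d_elig. With r = d_excl / d_elig,

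population effect / weighted estimate = (1 − q) + q × r.

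The documents give neither q nor r, so both are assumed over a range:

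| q | r = 0 | r = 0.5 | r = 1 | r = 1.5 |
|---|---|---|---|---|
| 0.2 | 0.80 | 0.90 | 1.00 | 1.10 |
| 0.4 | 0.60 | 0.80 | 1.00 | 1.20 |
| 0.6 | 0.40 | 0.70 | 1.00 | 1.30 |

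For example, q = 0.6 and r = 0.5 give 0.4 + 0.6 × 0.5 = 0.70. For any q above zero, the ratio is 1 only when r = 1, that is, when the average effect is the same in excluded and eligible smokers.

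**3. Is r = 1 plausible on the plan's own terms?** The ten-a-day rule was set to secure exposure to all four rotating labels. At 10 a day, 14 days use 140 cigarettes, or 7 packs of 20. The pack size is inferred from the 0 to 20 range of the evening-survey item on cigarettes left in the pack. At 5 a day, taken as an example, the figures are 70 cigarettes and 3.5 packs, so half as many packs and inserts. Users of other products were left out because the study was not designed to deal with substitution. Both reasons suggest that the effect may differ in the excluded groups. Neither says by how much.

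**4. Can the planned comparison reveal the problem?** No. The weighted and unweighted estimates are both averages over the same eligible participants, and d_excl enters neither. Their agreement or disagreement carries no information about excluded smokers.

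**The case against.** The strongest defence is that this is a sensitivity analysis on which no planned test depends. Models 1 to 5, which test H1 to H6, contain no weights, and no result in the SAP's Appendix 1 is labelled as weighted. This stands in full. A reader might infer that the trial's main conclusions are compromised, but the documents do not support that: the randomised comparisons keep their internal validity.

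Second, the SAP itself says that the comparison will serve to discuss limitations and differences from the wider population. This softens the claim but does not correct it, because both estimates come from the same eligible smokers.

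Third, the SAP names no benchmark, so weighting to totals for all smokers is inferred from the stated aim. That is fair. But whichever benchmark is chosen, the stated population is not covered.

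Fourth, calibration weights from this sample would also rest on unknown selection probabilities, and recruitment covered only a few areas. This is correct. It is why the weights should be called model-based, and why even the narrower claim depends on selection being explained by the weighting variables.

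A reader might also take the screening figures, 602 ineligible of 1818 (33%), as the share of smokers left uncovered. They cannot be used that way. They describe people who answered recruitment, not US smokers, and the documents do not break the 602 down by reason. Nor do the documents anchor any difference in effect between included and excluded smokers.

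**Conclusion.** The validity claim is wrong as written. No weight built from this sample can represent smokers whom the eligibility rules kept out. Reaching them takes an assumption of no effect modification by the exclusion variables, which the SAP does not state and the protocol's reason for the ten-a-day rule gives cause to doubt. That conclusion rests on the eligibility text alone and does not depend on any assumed number.

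The size of the error is unknown. Under the assumed 20% to 60% excluded share and an effect half as large in excluded smokers, the population effect would be 0.90 to 0.70 of the weighted estimate. If the effect in excluded smokers were larger than in eligible smokers, the error would run the other way. Severity is modest: what changes is the population to which the weighted result may be applied.

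**What to change.** In the SAP's Sensitivity Analysis section:

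- Restate the target as US adult smokers who meet the eligibility criteria that applied throughout: daily smoking, 10 or more cigarettes a day, no past-month use of e-cigarettes or other tobacco, and not pregnant or considering pregnancy.
- Name the benchmark data and the weighting variables. Filter the benchmark to that target as far as its variables allow, and list any criterion that cannot be applied.
- Describe the weights as model-based calibration (pseudo-) weights rather than probability weights. State the assumption that, given the weighting variables, selection among eligible smokers is unrelated to the treatment effect, and note the limited recruitment areas.
- State that excluded smokers are outside the inference, and that agreement between weighted and unweighted results is not evidence about them.

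The cost is a few sentences, a filter on the benchmark data and a narrower claim. No new data are needed, and the tests of H1 to H6 do not change.
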